1.2. Study Design

This study will evaluate the persistence of gE-specific immunogenicity after the primary 2-dose HZ/su vaccination in study ZOSTER-041 and the effect on immunogenicity and safety of revaccination with two additional doses of HZ/su vaccine after approximately 7 years in ZOSTER-041 in renal transplant (RT) subjects taking daily chronic immunosuppressive (CIS) therapy. Former study ZOSTER-041 subjects who received two doses of HZ/su vaccine were offered enrollment into study ZOSTER-073 at participating centers.

This study has three distinct phases:

- In the long-term follow-up (LTFU) phase, subjects will be followed for two years* (Day 1 to Month 24) in ZOSTER-073 study, which is approximately 4-7 years since primary vaccination in ZOSTER-041 study. Over the same time period, the occurrence of confirmed HZ cases and biopsy-proven RT rejections will be prospectively collected. Whereas the occurrence of confirmed/suspected HZ cases; and RT rejections, during the gap between studies ZOSTER-041 and ZOSTER-073, will be retrospectively collected back to subjects' study ZOSTER-041 last visit.

** Subjects who are ineligible for revaccination or unwilling to receive revaccination (hereafter referred to as non-revaccinated subjects) will be invited to be followed in an extension of the LTFU phase for a total of 4 years (Day 1 to Month 49) in ZOSTER-073 study, which is approximately 8-11 years since primary vaccination series in ZOSTER-041 study, with safety and immunogenicity assessments at study Months 37 and 49.*

- In the revaccination active phase (study Months 24 through 26), subjects will receive two additional doses of HZ/su vaccine, administered on a 1 to 2-month apart schedule at study Months 24 and 25. Safety and immunogenicity assessments will be performed 1 month post-revaccination Doses 1 and 2 at study Months 25 and 26, respectively.
- In the revaccination follow-up phase (study Month 26 to study end), safety and immunogenicity following revaccination will be prospectively monitored at study Months 37 and 49 (i.e., 12 and 24 months post-revaccination Dose 2).

Overview of Study Design

HZ/su = Herpes zoster subunit; LTFU = Long-term follow-up; Vacc 1-2 = Vaccination dose 1 & 2; re-Vacc 1-2 = Revaccinations dose 1 & 2

*The second dose of revaccination (Visit 4, study Month 25) will be administered 1 to 2 months after the first revaccination dose.

**Visit 5 (study Month 26), Visit 6 (study Month 37) and Visit 7 (study Month 49) will occur 1, 12 and 24 months after the second revaccination, respectively.

\$Phone contact will occur about 35 days before Visit 3 (study Month 24) to remind female subjects of childbearing potential to use adequate contraception.

Overview of Study Design Key Features

Design Features	
• Type of study: extension of other protocol(s); ZOSTER-041 for the analysis of long-term immunogenicity and safety.• Experimental design: Phase IIIB, open-label, uncontrolled, multi-centric, single group study.• Duration of the study: The study duration per subject will be approximately 49 months.
– Epoch 001: LTFU phase starting at Visit 1 (Day 1) and ending at Visit 3 (study Month 24)– Epoch 002: Revaccination phase starting at Visit 3 (study Month 24) and ending at Visit 7 (study Month 49)• Primary completion Date (PCD): Visit 5 (study Month 26). The date that the final subject was examined or received an intervention for the purpose of final collection of data for all primary outcomes, whether the clinical trial was concluded according to the pre-specified protocol or was terminated• End of Study (EoS): Last testing results released of samples collected up to Visit 7 (study Month 49).• Study group:
------------------------	---

Table 1 Study group, treatment, and epochs in the study

Study groups*	Target Number of subjects	Actual Number of subjects	Age (Min-Max)**	Treatment name	Epochs	
					From ZOSTER-041 primary study	Epoch 001 (open)
HZ/su	86	68	20 years - 82 years	HZ/su	•	•

HZ/su = Herpes Zoster subunit vaccine.

*HZ/su Group name for subjects who were vaccinated with 2 doses of HZ/su in study ZOSTER 041.

**Age at the first vaccination in study ZOSTER-041.

- **Control:** uncontrolled.
- **Revaccination schedule:** Subjects will receive two additional doses of the HZ/su vaccine, at Visit 3 (study Month 24) and at Visit 4 (study Month 25) in the revaccination phase.
- **Treatment allocation:** All eligible subjects will be enrolled into HZ/su group.
- **Blinding:** Open-label.
- **Sampling schedule:**
 - Blood samples to assess humoral immunogenicity will be collected from all subjects at Visit 1 (Day 1), Visit 2 (study Month 12), Visit 3 (study Month 24), Visit 4 (study Month 25)*, Visit 5 (study Month 26)*, Visit 6 (study Month 37) and Visit 7 (study Month 49).
 - Blood samples to assess CMI responses will be collected in the CMI sub-cohort at Visit 1 (Day 1), Visit 2 (study Month 12), Visit 3 (study Month 24), Visit 4 (study Month 25)*, Visit 5 (study Month 26)*, Visit 6 (study Month 37) and Visit 7 (study Month 49).
 - CCI [REDACTED]
 - [REDACTED]
 - [REDACTED]
 - [REDACTED]

*Blood samples will not be collected at Visit 4 (study Month 25) and Visit 5 (study Month 26) from non-revaccinated subjects.

- Clinical specimens of HZ lesions (from 3 separate lesions) will be collected from subjects clinically diagnosed as having a suspected case of HZ.

Overview of Study Design Key Features

- A urine sample (blood sample only if required by country, local or ethics committee regulations) will be collected from all female subjects of childbearing potential before revaccination at Visit 3 (study Month 24) and Visit 4 (study Month 25) for pregnancy testing.
- **Data collection:** electronic Case Report Form (eCRF).
 - Solicited and unsolicited AEs will be collected using a subject Diary (paper Diary) and transcribed into eCRF.
 - In the event of suspected HZ, the HZ clinical course will be collected using a HZ-specific Diary and Zoster Brief Pain Inventory (ZBPI) questionnaire and transcribed into eCRF.
- **Safety monitoring:** An internal safety review team (SRT, study team members) will review available safety data on a regular basis throughout the study. Any potential safety concern identified will be escalated to higher governing bodies as per internal GSK process.

Note: all ZOSTER-073 visits that are part of the LTFU phase (for both revaccinated and non-revaccinated subjects) will be displayed in terms of time since ZOSTER-041 primary vaccination series, which will be presented in 1 year intervals.

Since the interval between the end of ZOSTER-041 study and the start of this ZOSTER-073 study will vary per subject and is dependent on receipt of approval or implementing the study in the different participating countries, some results from the first ZOSTER-073 blood sample may correspond to year 4, year 5, or year 6 post vaccination. To be able to complement the modelling prediction by descriptive data analysis, yearly timeframes will be defined around the anniversary date post vaccination. The details of the set up for these intervals is described below.

The timeframe of first visit of the ZOSTER-073 study in LTFU phase will be computed between the date of the first visit of ZOSTER-073 study and the administration date of the second dose of primary series vaccination in the ZOSTER-041 study.

Time frame of first visit= (date of the first visit of ZOSTER-073 - date of vaccination dose 2 in ZOSTER-041+1) /365

The result of the first visit will be assigned to each yearly timeframe derived as follow

Timeframe of first visit	Lower bound of timeframe of first visit	Upper bound of timeframe of first visit
4	[3.5	<4.5)
5	[4.5	<5.5)
6	[5.5	<6.5)

The brackets indicate inclusive.

Yearly timeframe for the persistence analysis in the LTFU phase will be calculated by adding 1 year to the timeframe of first visit for each subsequent visit.

Example

	Primary series dose 2 – ZOSTER-041	Day 1- ZOSTER-073 Blood sample	time since primary series dose 2	assigned time frame for the ZOSTER-073 Visit 1 Day 1 blood sample	assigned time frame for the ZOSTER-073 Visit 2 blood sample	assigned time frame for the ZOSTER-073 Visit 3 blood sample
subject 1	1-nov-11	2-feb-16	4.260273973	4	5	6
subject 2	1-nov-11	5-jul-16	4.682191781	5	6	7

Similar computations will be performed for ZOSTER-073 Visit 6 and Visit 7 for non-revaccinated subjects.

Since pre-revaccination visits encompass a broad time range post-dose 2 of the primary series, the same interval may include one subject's data from ZOSTER-073 Visit 1 and another subject's Visit 2 data due to overlapping in timepoints by study year associated with the long-term follow-up phase.

Timepoints from ZOSTER-041 will be displayed in the immunogenicity summaries for both the LTFU phase and revaccination active and follow-up phases.

The following visits will appear in the immunogenicity summaries for the Per Protocol Set for analysis of persistence (LTFU phase). ZOSTER-041 Visits 1-5 and ZOSTER-073 Visits 1-3 will include data from both revaccinated and non-revaccinated subjects (prior to revaccination). ZOSTER-073 Visit 6 and Visit 7 will include data from non-revaccinated subjects only.

Study Phase	Subjects	Visit Number	SDTM.IS Visit Number	Study Month	Display	Description
ZOSTER-041	Revaccinated and Non-revaccinated	Visit 1	10	Month 0	PRE	Pre-vaccination (Month 0)
		Visit 2	20	Month 1	PI(M1)	Post-vaccination dose 1 (Month 1) – 1 month post-dose 1 ZOSTER-041

		Visit 3	30	Month 2	PII(M2)	Post-vaccination dose 2 (Month 2) – 1 month post-dose 2 ZOSTER-041
		Visit 4	50	Month 7	PII(M7)	Post-vaccination dose 2 (Month 7) – 6 months post-dose 2 ZOSTER-041
		Visit 5	70	Month 13	PII(M13)	Post-vaccination dose 2 (Month 13) – 12 months post-dose 2 ZOSTER-041
LTFU	Revaccinated and Non-revaccinated	Visit 1	10	Day 1	4YPD2	XYPD2= X years Post-vaccination dose 2 - from X.X up to less than X.X years post-vaccination dose 2 ZOSTER-041
		Visit 2	20	Month 12	5YPD2	
		Visit 3	30	Month 24	6YPD2	
	Non-revaccinated only	Visit 6	60	Month 37	7YPD2	
		Visit 7	70	Month 49	8YPD2	
					...	

Visit 1, Visit 2, and Visit 3 in the LTFU phase of ZOSTER-073 will also be presented as Day 1, Month 12, and Month 24, in accordance to the endpoint timepoints.

The following visits will appear in the immunogenicity summaries for the Per Protocol Set for immunogenicity after revaccination. Only data for revaccinated subjects will be included at all timepoints.

Study Phase	Subjects	Visit Number	SDTM.IS Visit Number	Study Month	Display	Description
ZOSTER-041	Revaccinated only	Visit 1	10	Month 0	PRE	Pre-vaccination (Month 0)
		Visit 2	20	Month 1	PI(M1)	Post-vaccination dose 1 (Month 1) – 1 month post-dose 1 ZOSTER-041
		Visit 3	30	Month 2	PII(M2)	Post-vaccination dose 2 (Month 2) – 1 month post-dose 2 ZOSTER-041

		Visit 4	50	Month 7	PII(M7)	Post-vaccination dose 2 (Month 7) – 6 months post-dose 2 ZOSTER-041
		Visit 5	70	Month 13	PII(M13)	Post-vaccination dose 2 (Month 13) – 12 months post-dose 2 ZOSTER-041
LTFU	Revaccinated only	Visit 1	10	Day 1	4YPD2 5YPD2 6YPD2 7YPD2 8YPD2 ...	XYPD2=X years Post-vaccination dose 2 - from X.X up to less than X.X years post-vaccination dose 2 ZOSTER-041
		Visit 2	20	Month 12		
		Visit 3	30	Month 24		
Revaccination active	Revaccinated only	Visit 3*	30	Month 24	PRE-RV	Pre-Revaccination baseline
		Visit 4	40	Month 25	1MPR1	Post-Revaccination Dose 1 (Month 1) 1 month post-revaccination 1
		Visit 5	50	Month 26	1MPR2	Post-Revaccination Dose 2 (Month 2) 1 month post-revaccination 2
Revaccination Follow-up	Revaccinated only	Visit 6	60	Month 37	12MPR2	Post-Revaccination Dose 2 (Month 13) 12 months, or 1 year, post-revaccination 2
		Visit 7	70	Month 49	24MPR2	Post-Revaccination Dose 2

						(Month 25) 24 months, or 2 years, post-revaccination 2
--	--	--	--	--	--	--

*If Visit 3 assessments are not available, Visit 2 or Visit 1 could be used as pre-revaccination baseline is the latest pre-revaccination dose assessment with a non-missing result from ZOSTER-073.

2. STATISTICAL HYPOTHESES

2.1. Hypothesis testing

All statistical analyses will be descriptive. No formal hypothesis testing will be conducted.

2.2. Multiplicity Adjustment

No statistical adjustment will be made for the interim or final analysis, which is intended to provide descriptive outputs in a phased manner, according to the relevant endpoint timepoints.

3. ANALYSIS SETS

Analysis Set	Description
Enrolled Set	All subjects with a complete vaccination course (2 doses of HZ/su vaccine) in study ZOSTER-041 who met the eligibility criteria and signed informed consent in the study ZOSTER-073.
Per Protocol Set (PPS) for analysis of persistence (LTFU phase from Visit 1 to Visit 3 for all subjects, and at Visit 6 and Visit 7 for non-revaccinated subjects)	The PPS for analysis of persistence will include evaluable subjects (i.e. those meeting all eligibility criteria, complying with the procedures and intervals defined in the protocol, with no elimination criteria) from the Enrolled Set for whom any persistence immunogenicity endpoints measures after primary vaccination course are available from Visit 1 (Day 1) to Visit 3 (study Month 24) regardless of revaccination status and at Visit 6 (study Month 37) and/or Visit 7 (study Month 49) for non-revaccinated subjects.
Exposed Set (ES) for revaccination phase	The ES for analysis of safety will include all subjects with at least one HZ/su vaccine dose administered in the study ZOSTER-073.
PPS for Immunogenicity after revaccination course (revaccination active phase)	The PPS for analysis of immunogenicity after revaccination will be defined by time-point and will include evaluable subjects (i.e. those meeting all eligibility criteria, complying with the procedures and intervals defined in the protocol, with no elimination criteria) from the ES for revaccination who have received 1 or 2 doses of revaccination up to the time point considered from Visit 3 (study Month 24) to Visit 5 (study Month 26) (i.e. 1 dose for Visit 4 and 2 doses for Visit 5) and have any immunogenicity endpoint measures available.
PPS for persistence after revaccination course (revaccination follow-up phase)	The PPS for persistence for analysis of immunogenicity after revaccination will include evaluable subjects (i.e. those meeting all eligibility criteria, complying with the procedures and intervals defined in the protocol, with no elimination criteria) from the ES for revaccination who received 2 doses of revaccination for whom persistence immunogenicity endpoints measures after revaccination course are available with any immunogenicity endpoint measures available from Visit 6 (study Month 37) to Visit 7 (study Month 49).

An adapted PPS for Immunogenicity after revaccination (revaccination active and follow-up phases) will be used in the tables to present revaccination Visits 3-7 together. The Enrolled Set will be used for LTFU phase safety analyses. For non-revaccinated subjects, the Enrolled Set will be used for analyses of safety and the PPS for analysis of persistence will be used for analyses of immunogenicity.

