6.2.1.1. Medical conditions

- Vaccination against HZ since completion of study ZOSTER-041.
- Significant underlying illness that, in the opinion of the investigator, is expected to prevent completion of the study.
- Any other condition that, in the opinion of the investigator, would interfere with the evaluations required by the study.

CONFIDENTIAL212340 (ZOSTER-073 EXT:041 Y4-10)
Protocol Amendment 1 Final**6.2.1.2. Prior/Concurrent clinical study experience**

- Concurrently participating in another interventional vaccine or immunosuppressive clinical study, in which the subject *is* exposed to an investigational or a non-investigational vaccine/product* (drug) *at any time during the ZOSTER-073 study.* **(Amended: 15 June 2020)**

*Allowed products: Immunosuppressant(s), which are investigational or non-registered product(s) at the local/country level, may be used if they are specifically prescribed for the prevention of allograft rejection and are:

- available locally through compassionate use programs,
- submitted for and pending local/country registration,
- approved and registered for use in one or more of the other participating countries with well-documented Summary of Product Characteristics (SPC) or Prescribing Information (PI).

The name of the active component(s) of these immunosuppressants must be provided in the concomitant medication listing.

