10.2. Populations for analyses

For purposes of analysis, the following analysis sets are defined [more detailed description will be provided in the statistical analysis plan (SAP)].

Analysis Set	Description
Enrolled Set	All subjects with a complete vaccination course (2 doses of HZ/su vaccine) in study ZOSTER-041 who met the eligibility criteria and signed informed consent in the current study.
PPS for analysis of persistence (LTFU phase from Visit 1 to Visit 3) (Amended: 15 June 2020)	The PPS for analysis of persistence will include evaluable subjects (i.e. those meeting all eligibility criteria, complying with the procedures and intervals defined in the protocol, with no elimination criteria) from the Enrolled set for whom persistence immunogenicity endpoints measures after primary vaccination course are available from Visit 1 (Day 1) to Visit 3 (Month 24). (Amended: 15 June 2020)
ES for revaccination phase	The ES for analysis of safety will include all subjects with at least one HZ/su vaccine dose administered in the study ZOSTER-073.
PPS for Immunogenicity after revaccination course (revaccination active phase)	The PPS for analysis of immunogenicity after revaccination will be defined by time-point and will include evaluable subjects (i.e. those meeting all eligibility criteria, complying with the procedures and intervals defined in the protocol, with no elimination criteria) from the ES for revaccination who have received one or two doses of revaccination schedule up to the time point considered from Visit 3 to Visit 5 (Month 26). (Amended: 15 June 2020)
PPS for persistence after revaccination course (revaccination follow-up phase)	The PPS for persistence for analysis of immunogenicity after revaccination will include evaluable subjects (i.e. those meeting all eligibility criteria, complying with the procedures and intervals defined in the protocol, with no elimination criteria) from the ES for revaccination for whom persistence immunogenicity endpoints measures after revaccination course are available from Visit 6 (Month 37) to Visit 7 (Month 49). (Amended: 15 June 2020)

PPS = per protocol set, ES = exposed set

For non-revaccinated subjects, the enrolled set will be used for analyses of safety and immunogenicity. Details will be described in the statistical analysis plan (SAP). (Amended: 15 June 2020)

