	An adverse event (AE) can therefore be any unfavourable and unintended sign (including an abnormal laboratory finding), symptom, or disease (new or exacerbated) temporally associated with the use of a medicinal product. For marketed medicinal products, this also includes failure to produce expected benefits (i.e. lack of efficacy), abuse or misuse.
Adverse Events of Special Interest (AESIs):	AESIs are a subset of AEs/SAEs that include specific disorders of interest which may or may not be related to vaccination. For this trial, AESIs will be defined as potential immune-mediated disorders and renal allograft rejection.
Anamnestic:	Relating to a rapid increased production of antibodies in response to a previously experienced immunogenic substance.
Blinding:	A procedure in which 1 or more parties to the trial are kept unaware of the treatment assignment in order to reduce the risk of biased study outcomes. The level of blinding is maintained throughout the conduct of the trial, and only when the data are cleaned to an acceptable level of quality will appropriate personnel be unblinded or when required in case of a serious adverse event. In an open-label study, no blind is used. Both the investigator and the subject know the identity of the treatment assigned.
Certified copy:	A copy (irrespective of the type of media used) of the original record that has been verified (i.e. by a dated signature or by generation through a validated process) to have the same information, including data that describe the context, content, and structure, as the original.
Donor-specific antibodies:	Anti-HLA antibodies specifically produced against a donor organ's foreign HLA antigens. Other anti-HLA antibodies may be produced against foreign HLA antigens from blood transfusion, child birth, or previous organ transplant.
Eligible:	Qualified for enrollment into the study based upon strict adherence to inclusion/exclusion criteria.

CONFIDENTIAL

212340 (ZOSTER-073 EXT:041 Y4-10)
Protocol Amendment 1 Final

End of Study (EoS) (Synonym of End of Trial)	For studies with collection of human biological samples and/or imaging data, the EoS is defined as Last testing results released of samples collected up to Visit 7* * In this case EoS must be achieved no later than 8 months after LSLV.

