Code	Condition under which the code is used	Analysis set eliminated from	Visit (timepoints) where the code is applicable	Type of Elimination
	revaccinated without fulfilling the eligibility criteria for revaccination	(revacc. follow-up phase)		
2040	Administration of any concomitant medication(s) forbidden by the protocol	PPS (revacc. active phase), PPS (revacc. follow-up phase)	Visit 1 – Visit 7	Eliminate from Visit(s) only, as applicable
2050	Underlying medical condition forbidden by the protocol, or some Intercurrent medical conditions (IMCs). (To be determined before analysis during data management review (DMR))	PPS (LTFU), PPS (revacc. active phase), PPS (revacc. follow-up phase)	Visit 1 – Visit 7 (visit and onward)	Eliminate from Visit and onwards
2060	Concomitant infection related to the revaccination which may influence immune response – For example, clinically diagnosed suspected HZ cases before Visit 1 or PCR confirmed HZ cases after Visit 1	PPS (LTFU), PPS (revacc. active phase), PPS (revacc. follow-up phase)	Visit 1 – Visit 7	Eliminate from Visit(s) only, as applicable
2070	Concomitant infection not related to the vaccine which may influence immune response – For example, in case of revaccination, any additional confirmed or suspected immunosuppressive or immunodeficient condition (e.g., malignancy, hepatitis, HIV infection, systemic infection)	PPS (LTFU), PPS (revacc. active phase), PPS (revacc. follow-up phase)	Visit 1 – Visit 7	Eliminate from Visit and onwards
2080	Out of window treatment administration – Revaccination dose 1 (study Month 24) to revaccination dose 2 (study Month 25) outside 25-90 day interval	PPS (revacc. active phase), PPS (revacc. follow-up phase)	Visit 3 – Visit 4	Eliminate from Visit and onwards
2090	Missed Visit, excluding phone contact Note: this does not apply to delayed enrolled subjects who had their Visit 1 and Visit 2 on the same day.	PPS (LTFU), PPS (revacc. active phase), PPS (revacc. follow-up phase)	Visit 1 – Visit 7	Eliminate from Visit only
2090	Assessment not properly performed – For example, incomplete assessment, missed assessment except safety follow-up Note: this does not apply to delayed enrolled subjects who had their Visit 1 and Visit 2 on the same day. These subjects would have to have an assessment at either Visit 1 or Visit 2.	PPS (LTFU), PPS (revacc. active phase), PPS (revacc. follow-up phase)	Visit 1 – Visit 7	Eliminate from Visit only

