4.2. Primary Endpoints Analyses

The primary immunogenicity analysis for the LTFU phase will be performed using the PPS for analysis of persistence (LTFU phase from Visit 1 to Visit 3 for all subjects, and at Visit 6 and Visit 7 for non-revaccinated subjects). If 5% subjects or more with serological results are eliminated from the PPS for analysis of persistence, then a complementary analysis will be performed on the Enrolled Set.

The primary immunogenicity analysis for the revaccination active phase will be performed on the PPS for immunogenicity after revaccination course (revaccination active phase). If 5% subjects or more with serological results are eliminated from the PPS for revaccination active phase, then a complementary analysis will be performed on the Exposed Set.

All analyses will be performed overall.

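### The Enrolled Set is conditional on eligibility, so a subject enrolled in error drops out of the LTFU and non-revaccinated safety tables and of the analysis meant to complement the LTFU per-protocol set

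*SAP*

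**What the plan says.** SAP section 3 defines the Enrolled Set by three conditions: a complete two-dose course in ZOSTER-041, eligibility, and consent. The last two read "who met the eligibility criteria and signed informed consent in the study ZOSTER-073". Protocol 10.2 has the same rule, "who met the eligibility criteria and signed informed consent in the current study", so this is not a slip in the SAP. The protocol glossary (12.1.2) defines eligible as "Qualified for enrollment into the study based upon strict adherence to inclusion/exclusion criteria".

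The set has several uses:

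- LTFU safety: "The Enrolled Set will be used for LTFU phase safety analyses" (SAP 3, repeated in 4.3.2). The tables in 4.3.2.1 cover related SAEs, allograft rejections, HZ cases and declining graft function.
- Non-revaccinated subjects: "For non-revaccinated subjects, the Enrolled Set will be used for analyses of safety" (SAP 3). SAP 4.5 adds that these subjects will be compared with revaccinated subjects after Visit 3.
- LTFU immunogenicity: if 5% or more of subjects with serology are eliminated from the persistence PPS, "then a complementary analysis will be performed on the Enrolled Set" (SAP 4.2).
- Disposition: SAP 6.1.1 runs the flow from the Enrolled Set to each PPS and to the Exposed Set.

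The Exposed Set takes every subject with at least one ZOSTER-073 dose and has no eligibility condition. In SAP 3.1 only codes 800 (fraud) and 900 (consent) remove a subject from all sets. Code 2010 is for an ineligible subject "revaccinated without fulfilling the eligibility criteria for revaccination" and acts on the two revaccination PPSs.

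**The concern.** An enrolled set normally records who entered the study and was followed. Eligibility is then a per-protocol matter. Here the eligibility condition sits in the base population, with three consequences.

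First, safety data already collected from a subject enrolled in error would not be counted in the LTFU or non-revaccinated tables. These are small tables of rare events, where one subject can decide whether a row reads zero.

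Second, the complementary analysis exists to show what the per-protocol exclusions did. The persistence PPS already requires eligibility and is drawn from the Enrolled Set. A subject excluded for ineligibility is therefore missing from both analyses, and comparing them says nothing about that kind of exclusion.

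Third, the plan applies different standards to its two safety populations, and its definition and its code table can give different denominators for the same table.

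**Working it through.** No figure in the plan depends on this definition. The nearest one, the target of 73 evaluable subjects, reproduces (86 × 0.85 = 73.1) and is not affected.

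**Tracing two hypothetical subjects.** Each received two ZOSTER-041 doses, gave valid consent, and was enrolled without meeting a Visit 1 criterion.

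| | Never revaccinated | Revaccinated |
|---|---|---|
| Enrolled Set, by the SAP 3 definition | out | out |
| Enrolled Set, by the SAP 3.1 codes | in (neither 800 nor 900 applies) | in |
| Persistence PPS, by definition | out | out |
| Exposed Set | out (no dose) | in |
| Revaccination PPSs | out | out (definition; code 2010) |

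By the definition, the first subject belongs to no analysis set at all. The second is in the Exposed Set but not in the Enrolled Set, so the disposition flow of SAP 6.1.1 does not nest. That subject's events before revaccination are lost, while later ones are counted. A programmer working from the codes would keep both subjects in the Enrolled Set.

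**Effect on a safety percentage.** Inputs: 68 subjects (SAP 1.2, Table 1, actual number) and exact Clopper-Pearson 95% intervals (SAP 4.1.1). Limits for x events in n subjects: lower = Beta quantile 0.025 with parameters (x, n − x + 1); upper = Beta quantile 0.975 with parameters (x + 1, n − x). For x = 0 the lower limit is 0 and the upper is 1 − 0.025^(1/n). Assumptions: the 68 are all who entered, exactly one was enrolled in error, and that subject had an event.

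- That event is the only one. Kept: 1/68 = 1.5% (0.04 to 7.9). Removed: 0/67 = 0%, upper limit 1 − 0.025^(1/67) = 5.4%.
- There are two events, one of them in that subject. Kept: 2/68 = 2.9% (0.4 to 10.2). Removed: 1/67 = 1.5% (0.04 to 8.0).

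In the non-revaccinated tables one subject weighs more than 1/68, but the documents do not give that denominator.

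**Effect on the 5% trigger.** Assume all 68 have serology and the percentage is taken within the Enrolled Set. Three exclusions give 3/68 = 4.4%, below the trigger; four give 4/68 = 5.9%, above it. If one of the four is ineligible and already outside the Enrolled Set, the count is (4 − 1)/(68 − 1) = 3/67 = 4.5%, and the complementary analysis is not run.

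**The case against.** The strongest reply is that the plan's usage points to a milder meaning. The PPS definition selects eligible subjects from the Enrolled Set, which would be redundant if that set held only eligible subjects. Protocol 10.1.1 and SAP 5 gloss eligibility for enrolment as having had two ZOSTER-041 doses. The code table, which identifies who is eliminated, has no code removing anyone from the Enrolled Set for ineligibility. These points show that the intention may be benign, but they do not settle the text. The set definition lists the two doses separately from the eligibility criteria, so the gloss makes that phrase redundant in turn, and the mismatch with the codes is part of the problem.

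Three stronger readings are tempting, and the documents do not support them.

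- *Joining another study later removes a subject retrospectively.* The concurrent-study exclusion does run "at any time during the ZOSTER-073 study" (Protocol 6.2.1.2). But Protocol 6.1.1 and 6.2.1 place the enrolment criteria at study entry, and Protocol 7.5.2 says that use of an investigational product during the study affects per-protocol evaluability without requiring withdrawal. The recheck at Visit 3 (Protocol 6.2.2) decides only whether the subject is revaccinated.
- *Enrolment ineligibility has no per-protocol route.* The PPS definition itself requires eligibility. Codes 1040 (forbidden vaccines) and 2050 (forbidden medical conditions) act on PPS (LTFU) and plausibly cover much of the enrolment list. Code 2010 reaches enrolment criteria for revaccinated subjects, because Protocol 6.1.2 and 6.2.2 carry those criteria forward. What is missing is an explicit enrolment-eligibility code for PPS (LTFU).
- *Revaccination safety is affected.* It uses the Exposed Set and is not.

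It is also fair to say that SAP 6.1.3 summarises deviations that cause exclusion from a set, so the exclusion would be visible. The excluded subject's events would still not be in the percentages.

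**Conclusion.** The point holds for subjects enrolled without meeting the Visit 1 criteria. If the definition is followed as written, such a subject is absent from the LTFU and non-revaccinated safety tables and from the complementary LTFU analysis. The definition conflicts with the code table and is stricter than the Exposed Set.

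The size is small per subject, about 1.5 percentage points of a denominator of 68, but enough to turn a single observed event into none. It rests on at least one subject having been enrolled in error, which the documents do not report; the number may be zero, and then no result changes. The intervals in the illustration overlap widely and the study is descriptive, so no test result is at stake. A reader might infer that safety data have been lost; the documents show only a rule that would lose them.

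**What to change.** - Define the Enrolled Set as all subjects with two HZ/su doses in ZOSTER-041 who signed consent and entered ZOSTER-073, whether or not they were later found ineligible. Codes 800 and 900 continue to act on all sets.
- Apply enrolment ineligibility through the PPS only, by extending code 2010 to PPS (LTFU) from Visit 1.
- Keep LTFU safety, non-revaccinated safety, disposition and the complementary analysis on the redefined set. The Exposed Set then nests within it.
- Record the departure from Protocol 10.2 in SAP 4.8, which already records a change to the persistence PPS.

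The cost is one definition, one line in the code table and one entry in SAP 4.8, settled before the data management review that fixes the eliminations. No new data are needed.
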